- No study treatment will be given during the post-treatment follow-up epoch; however, patients are allowed to take background medication and rescue medication. If a subject relapses i.e. develops symptoms with an UAS7 ≥ 12 , the investigator should be contacted for an ad-hoc visit to consider treatment with standard of care or other therapy.

Figure 3-1 Study design

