9.7 Sample size calculation

It is expected that approximately 240 patients will enter the extension study. The following graph shows the binomial probability of observing at least one event for a range of true incidences from 0.001 (0.1%) to 0.05 (5%) in samples of 200, 250 and 300 patients.

Figure 9-1 Probability of observing adverse events with given incidence

10 Ethical considerations

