2.5.5 Statistical model, hypothesis, and method of analysis

No hypotheses will be tested as per the protocol. All the analysis will have a descriptive purpose.

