2.6.10 Missing data handling and censoring process

There are 17 patients taking concomitant medication of omalizumab post treatment, which would have impact on the estimated efficacy during the post treatment period, especially for the patients stay in the follow-up period until the end of the study. In order to exclude the potential bias causing by the omalizumab use during post-treatment period, the efficacy data observed after start concomitant use of omalizumab will be set as missing.

Missing data handling of all weekly score coming from UPDD [REDACTED].

The weekly score (HSS7, ISS7, sleep/activity interference scores) will be derived by adding up the average daily scores of the 7 days preceding the visit. The weekly score will then range from 0 to 21. If one of the morning or evening score is missing, then the non-missing score for that day (morning or evening) will be used as the daily score.

For each weekly score from UPDD [REDACTED], except weekly total rescue medication, if one or more of the daily scores are missing, then the following principles will be applied to handle the missing data:

- If a patient has at least 4 non-missing daily scores within the 7 days prior to the study visit, then the weekly score will be calculated as the sum of the available eDiary scores of that week, divided by the number of non-missing days multiplied by 7.
- If there are less than 4 non-missing daily scores within the prior 7 days, then the weekly score will be missing for that week.

For rescue medication, if one or more of the daily number of tablets are missing, then the total weekly number of tablets will be missing.

The weekly Urticaria Activity Score is the sum of both the HSS7 score and the ISS7 score and will be missing if at least one of them is missing.

For all display of response rate by week, the rate will be obtained by dividing the number of responses by the total number of patients in the group analyzed, whatever if some of these patients analyzed have missing data on this week or not.

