For the response rate analysis, for patients with missing data either due to discontinuation or due to insufficient eDiary data during that week or the start concomitant use of omalizumab, data imputation of the response will be done using the worst-case scenario (i.e. non-responder). For the patients completing the study, there will be no more imputation applied after the end of study visit. For the patients discontinuing the study early or start concomitant use of omalizumab, the imputation will be applied up to Week 100.

Duplicate data handling of questionnaires

For HSS7, ISS7 and UAS7, the daily score is derived from the average of morning and evening scores. All other questionnaires are completed either daily or at visits. If any of those questionnaires are completed more than once per day or visit (depending on the questionnaire schedule), then the worst outcome (i.e. the highest score) of the duplicate observations will be used in the analysis.

Censoring of time to response.

Time endpoints, such as time to first complete hives response, will be considered censored at the date of the last non-missing weekly score up to E1 Week 52, for any non-responder.

Censoring of time to loss of response.

For any patient maintaining response, the time to loss, such as time to first loss of complete hives response for patients who completed the treatment epoch and achieved complete hives response at Week 52, will be considered censored at the date of the last non-missing weekly score or at the date of start concomitant use of omalizumab.

Note that time to loss of response will be missing for all patients without having achieved the response in the E1 treatment period at study week 52.

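### Week 52 responders who start omalizumab with no recorded loss are censored in the time-to-loss curves, although the same SAP section scores that start as non-response

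*SAP*

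**What the plan says.** The secondary objective is sustained remission: UAS7 of 6 or less held through the 48-week follow-up among patients in remission at the end of treatment (Protocol 2.2, SAP 1.2.2). Its time-to-event form is the Kaplan-Meier time to UAS7 > 6 in Week 52 remitters (SAP Table 1-6 and 2.6.3). Parallel curves cover loss of UAS7 = 0 and loss of HSS7 = 0.

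SAP 2.6.10 handles omalizumab in two ways.

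- **Response rates.** For patients with missing data, including data missing because omalizumab was started, "data imputation of the response will be done using the worst-case scenario (i.e. non-responder". On duration: "For the patients discontinuing the study early or start concomitant use of omalizumab, the imputation will be applied up to Week 100".
- **Time to loss.** The rule opens with "For any patient maintaining response, the time to loss, such as time to first loss of complete hives response" and states that such a patient "will be considered censored at the date of the last non-missing weekly score or at the date of start concomitant use of omalizumab". The hives curve is given as an example, so the rule also governs time to UAS7 > 6.

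The section gives the scale, "There are 17 patients taking concomitant medication of omalizumab post treatment", and the motive, which is to keep the effect of omalizumab out of the post-treatment efficacy results.

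The cut-off is stated in two ways. SAP 2.6.1 to 2.6.3 and 2.6.10 use the date omalizumab starts. SAP section 4 uses the last visit before that date.

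**The concern.** Kaplan-Meier censoring assumes that a patient removed from the risk set has the same later risk of loss as those who remain. That is doubtful for someone who has just started a new biologic for the disease under study. Protocol 3.1 places other therapy in follow-up in the context of relapse: "the investigator should be contacted for an ad-hoc visit to consider treatment with standard of care or other therapy". If omalizumab was started because disease was returning, the censoring is informative and the remission curve reads too high.

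The visible SAP text does not say why the same event is a failure in one analysis and uninformative in the other. It also plans no sensitivity analysis that counts the start as a loss. At stake is the durability estimate for the only stated secondary objective. The curve and the weekly rates could also give conflicting accounts of the same patients.

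**Working it through.** No figure in the documents depends on this rule, so there is none to reproduce.

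**Who is affected**

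1. Not in response at Week 52: outside the time-to-loss analysis (SAP 2.6.10).
2. In response at Week 52, with a weekly score above threshold before omalizumab: no longer maintaining response, so already an event.
3. In response at Week 52, no recorded score above threshold, then omalizumab: censored. Call this number k.

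Only the third group matters. The documents give 17 users in total and no breakdown, so k is between 0 and 17. The enrolment figure is an expectation: "It is expected that approximately 240 patients will enter the extension study". The upper limit is therefore 17/240 = 7.1% of expected enrolment.

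**Size, with assumed inputs**

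Let m be the remitters at Week 52 and L the ordinary losses over 48 weeks. Neither is in the documents. I assume m = 120 and L = 60, with losses spread evenly over weeks 1 to 48 after Week 52 and omalizumab starts spread evenly over weeks 4 to 44.

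- Start counted as a loss: S = (m − L − k)/m.
- Start censored: S = product of (1 − 1/r) over the ordinary losses, where r is the number still at risk. By hand, S lies between (m − k − L)/(m − k), if all k leave before the first loss, and (m − L)/m, if all leave after the last.

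| k | Counted as loss | Censored: limits | Censored: even spread | Difference |
|---|---|---|---|---|
| 0 | 60/120 = 50.0% | 50.0% | 50.0% | 0 |
| 6 | 54/120 = 45.0% | 54/114 = 47.4% to 50.0% | 48.3% | 3.3 points |
| 17 | 43/120 = 35.8% | 43/103 = 41.7% to 50.0% | 44.7% | 8.9 points |

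With m at 80, 120 and 160, ordinary losses at 30%, 50% and 70% of m, and k from 3 to 17, the censored curve is higher by 1.0 to 16.7 points. The top value needs m = 80, 30% losses and k = 17, which is an extreme.

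**The section 4 cut-off**

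Follow-up visits are 12 weeks apart (Protocol 3.1). Take a remitter last seen at Week 52, with UAS7 > 6 in Week 60 and omalizumab in Week 62. Cutting at the start date keeps a loss at Week 60. Cutting at the previous visit discards that score and censors the patient at Week 52. With 120 remitters, 60 other losses and 6 such patients (all assumed), the estimate moves from 54/120 = 45.0% to 54/114 = 47.4%. Under this cut-off, group 2 is no longer safe.

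**The case against.** The strongest reply is that few patients may be affected. Protocol relapse is UAS7 of 12 or more, well above the loss threshold of 6. The diary is completed daily and SAP 2.1.3 defines a score week for every 7 days, so a patient who relapses and is then treated would normally have crossed 6 first. Protocol 5.6.1 also advises at least 4 months of wash-out before omalizumab. Four months is about 17 weeks. Counted from the last scheduled dose at Week 48, that leaves about 13 weekly scores after Week 52 in which a loss could be recorded. This stands as a limit on the size, although the wash-out is only advice and the argument needs diary data and the start-date cut-off.

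A reader might infer that every omalizumab starter is treated as if still able to be in remission. The documents do not support that, because the rule reaches only patients still maintaining response.

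A reader might also infer that angioedema, which UAS7 does not measure, brought remitters to omalizumab. Protocol 1.1 reports angioedema with 33-67% of CSU cases, but no document says that omalizumab was started for it, or that it occurred without hives or itch in remitters. Diary gaps are a firmer route, since a week with fewer than 4 daily scores has no weekly score. Even so, every week from true loss to omalizumab would have to be missing or below threshold.

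Censoring can also be a deliberate choice that asks what would have happened without omalizumab. The rates and the curve use different denominators and may answer different questions, and the non-responder rates for UAS7 of 6 or less are already planned through follow-up. That is fair, but the visible text neither names such a strategy nor justifies it beside the non-responder rule. Parts of Table 1-6 and SAP 2.6.3 are redacted, so a further relapse analysis cannot be ruled out.

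**Conclusion.** The inconsistency is in the text. For Week 52 responders who start omalizumab with no recorded loss, and for them only, censoring is likely to be informative and can bias durability of remission upwards. The direction rests on the start being disease-driven, and the documents do not give the reasons for starting.

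The size cannot be determined from the documents. The effect is zero if every starter had a recorded loss first, and every percentage-point figure above rests on assumed values of m, L, k and event times. A large bias should not be claimed.

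The section 4 cut-off is a separate conflict. If applied, it could turn recorded losses into censored times.

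This is a worthwhile correction to a secondary, descriptive analysis ("No hypotheses will be tested as per the protocol"). It does not affect the primary safety objective.

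**What to change.** 1. Use the date of omalizumab start as the single cut-off throughout the SAP, and align section 4 with 2.6.1 to 2.6.3 and 2.6.10, so that earlier recorded losses stay as events.
2. In 2.6.10, define loss as the earlier of the first weekly score above threshold or omalizumab start, in line with the non-responder rule. Censor patients with neither at the last non-missing score. Keep the present censored curve as a sensitivity analysis. At minimum, pre-specify the composite version beside the censored one and state the reason for each.
3. Report how many of the 17 were Week 52 remitters, and how many of those had no UAS7 > 6 before starting omalizumab.

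The cost is a few sentences and a change to the event flag, with no new data. The durability estimate will be equal or lower, and omalizumab started for reasons other than relapse would count as a loss. The retained censored curve shows how much that matters.

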2.8 Interim analysis

The study is planned with one interim analysis occurring when all patients have completed the treatment epoch. In particular, the summary will include baseline characteristics, adverse events, exposure, concomitant medication, ECG, vital signs, safety laboratory data and the weekly symptom scores, derived responder status, [REDACTED].

Study procedures will not be modified as a result of this interim analysis.

3 Sample size calculation

The sample size calculation is defined in the protocol [\[section 9.7\]](#).

4 Change to protocol specified analyses

- The definition of the safety set (SS) was updated - no additional check needed for subjects “who had at least one post-baseline (Visit 301) safety assessment”.
- Medical history will consist of medical conditions which started before the start of the core study, instead of before the start of the open-label extension study and will therefore only be listed and not tabulated.
- Adjudicated AEs will only be listed and not summarized, since few adjudicated AEs are expected.

[REDACTED]

- [REDACTED]
- [REDACTED]
- The definition of TEAE is updated as: all adverse events which start after the first dose of study medication in the extension study and within 16 weeks of last dose, or events present prior to the first dose of extension study treatment and increased in severity (within 16 weeks of last dose).
- All adverse events which start after the first dose of study medication in the extension study or events present prior to the first dose of extension study treatment and increased in severity, will be considered TEAEs, similar to the core study definition. TEAEs will be summarized by treatment epoch and over all, which will be based on the epoch derivation that depends on the patient's visit dates which might not occur exactly on last dose + 4 weeks.
- For patients with concomitant use of omalizumab, efficacy variables (HSS/ISS/UAS/ [REDACTED]) will be censored at the last visit prior to the date of start of omalizumab and treated as missing onward.
- Only positively adjudicated Cerebrovascular events will be listed.

5 Appendix

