2.6.1 Hives Severity Score (HSS7)

The number of hives will be recorded by the patient twice daily in their eDiary on a scale of 0 (none) to 3 (severe (greater than 12 hives)).

A weekly score (HSS7) will be derived by adding up the average daily scores of the 7 days. The weekly score will therefore range from 0 to 21. If one of the morning or evening scores is missing, then the non-missing score for that day (morning or evening) will be used as the daily score. Complete hives response is defined as $HSS7 = 0$.

Changes from baseline in HSS7 score will be computed and will be summarized along with the absolute values at each visit. Mean with 95% confidence interval will be displayed graphically over time to describe the score change during the study. In addition, HSS7 descriptive statistics will be summarized, [REDACTED].

For $HSS7=0$ response, summary tables and graphs by visit will display, the response rate with the 95% Clopper-Pearson exact confidence interval. In addition, $HSS7=0$ response will be summarized, [REDACTED].

Kaplan-Meier estimates of the time to first $HSS7=0$ response and of the time to first loss of response for patients having achieved response at Week 52, will be plotted and will be tabulated at defined time points.

For patients with concomitant use of omalizumab, HSS scores will be censored at the date of start of omalizumab and treated as missing onward.

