2.6.2 Itch Severity Score (ISS7)

The severity of the itch will be recorded by the patient twice daily in their eDiary, on a scale of 0 (none) to 3 (intense/severe).

A weekly score (ISS7) will be derived by adding up the average daily scores of the 7 days preceding the visit. The weekly score will therefore range from 0 to 21. Partially missing diary entries will be handled in the same way as described for the hives severity score. Complete itch response is defined as $ISS7 = 0$.

Changes from baseline in ISS7 score will be computed and will be summarized along with the absolute values at each visit. Mean with 95% confidence interval will be displayed graphically over time to describe the score change during the study. In addition, ISS7 descriptive statistics will be summarized, [REDACTED].

$ISS7=0$ response will be summarized and plotted by visit and response rate with the 95% Clopper-Pearson exact confidence interval will be included in the analysis. In addition, $ISS7=0$ response will be summarized, [REDACTED].

For patients with concomitant use of omalizumab, ISS scores will be censored at the date of start of omalizumab and treated as missing onward.

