2.6.3 The weekly Urticaria Activity Score (UAS7)

[figure not shown]
The UAS7 is the sum of the HSS7 score and the ISS7 score. The weekly UAS7 score will then range from 0 to 42. Complete UAS7 response is defined as $UAS7 = 0$.

[figure not shown]
Changes from baseline in UAS7 score will be computed and will be summarized along with the absolute values at each visit. Mean with 95% confidence interval will be displayed graphically over time to describe the score change during the study. In addition, UAS7 descriptive statistics will be summarized, [REDACTED].

[figure not shown]
UAS7=0 response will be summarized and plotted by visit and response rate with the 95% Clopper-Pearson exact confidence interval will be included in the analysis. In addition, achievement of UAS7 ≤ 6 will be summarized similarly. Also, UAS7=0 response will be summarized, [REDACTED].

Kaplan-Meier estimates of the time to first UAS7=0 response and of the time to first loss of response for patients having achieved response at Week 52, will be plotted and will be tabulated at defined time points. In addition, Kaplan-Meier estimates of the time to first UAS7 > 6 for patients having achieved UAS7 ≤ 6 at Week 52 [REDACTED], will be tabulated at defined time points.

For patients with concomitant use of omalizumab, UAS scores will be censored at the date of start of omalizumab and treated as missing onward.

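### SAP Section 4 cuts efficacy scores off at the last visit before omalizumab, Section 2.6 at the omalizumab start date, so a relapse recorded in between can be lost

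*SAP*

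**What the plan says.** Sections 2.6.1, 2.6.2 and 2.6.3 of the SAP give one rule for the three diary scores: "HSS scores will be censored at the date of start of omalizumab and treated as missing onward", "ISS scores will be censored at the date of start of omalizumab and treated as missing onward" and "UAS scores will be censored at the date of start of omalizumab and treated as missing onward".

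Section 2.6.10 agrees. It reports that "There are 17 patients taking concomitant medication of omalizumab post treatment", and to keep omalizumab from biasing the follow-up results it provides that "the efficacy data observed after start concomitant use of omalizumab will be set as missing". For time to loss of response, a patient who is maintaining response "will be considered censored at the date of the last non-missing weekly score or at the date of start concomitant use of omalizumab".

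Section 4, which lists changes from the protocol's analyses, has a bullet on the same variables and the same patients. There the data "will be censored at the last visit prior to the date of start of omalizumab and treated as missing onward".

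Section 4 is operative text, not a version history. Nothing visible in the SAP ranks it above or below Section 2.6.

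**The concern.** The start date and the last visit before it can be almost 12 weeks apart in follow-up, and weekly diary scores are recorded throughout that time. A patient's first UAS7 above 6 can therefore fall after the last visit and before omalizumab. The Section 2.6 rule keeps it as an event. The Section 4 rule deletes it, and the patient leaves the risk set as a remitter.

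Sustained remission off treatment is the only secondary objective (SAP 1.2.2). The visible analysis restricted to patients in remission at Week 52 is the Kaplan-Meier analysis of time to UAS7 above 6 (SAP Table 1-6 and 2.6.3). The curves for loss of UAS7 = 0 and loss of HSS7 = 0 are exposed in the same way. Two programmers following this SAP could report different figures.

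**Working it through.** **1. Width of the gap.** SAP Table 1-1 schedules the follow-up visits on Days 365, 449, 533, 617 and 701. The differences are 449 − 365 = 533 − 449 = 617 − 533 = 701 − 617 = 84 days, or 12 weeks.

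**2. Do scores exist between visits?** SAP 2.1.3 defines every study week w as Days 7(w − 1) + 1 to 7w. Section 2.6.10 speaks of the rate "For all display of response rate by week" and of the last non-missing weekly score. On that reading, scores are weekly throughout follow-up.

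**3. Data at risk.** For each possible start day from 366 to 701, I counted the complete study weeks between the last scheduled visit and the start day. The maximum is 12 and the mean is 5.6 if start days are spread evenly. At least one complete week falls in the gap for 93% of start days. For 17 users:

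- ceiling: 17 × 12 = 204 patient-weeks
- planned follow-up: 240 × 48 = 11,520 patient-weeks
- share: 204 / 11,520 = 1.8%

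The share is small, but these weeks are not a random sample. Protocol 3.1 links other therapy to relapse, so they fall where relapse is plausible.

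**4. One patient under both rules.** Remission at Weeks 52 and 64, first UAS7 above 6 in Week 69, omalizumab in Week 73. Section 2.6 gives an event at Week 69. Section 4 gives censoring at Week 64, the last scheduled visit before omalizumab.

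**5. Effect on the Kaplan-Meier estimate (illustration).** The documents do not say how many users were in remission at Week 52, how many had a UAS7 above 6 first, or how long afterwards omalizumab began. The assumed inputs are:

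- 100 remitters, 8 of them omalizumab users;
- exponential relapse in whole weeks, with true 48-week remission of 30% or 50%;
- a share f of users who start omalizumab L weeks after their first UAS7 above 6, but not before Week 65 (last dose at Week 48 plus the 4-month wash-out advised in Protocol 5.6.1);
- the other users start evenly over follow-up weeks 13 to 47, with no earlier event.

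Change in estimated remission at Week 100, Section 4 rule minus start-date rule, in percentage points (30% / 50% true remission):

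| Lag L | f = 0 | f = 0.5 | f = 1 |
|---|---|---|---|
| 2 weeks | −0.88 / −0.60 | +0.82 / +1.47 | +2.45 / +3.49 |
| 4 weeks | −0.87 / −0.60 | +0.63 / +1.18 | +2.02 / +2.88 |
| 8 weeks | −0.88 / −0.60 | +0.16 / +0.52 | +1.10 / +1.54 |

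At L = 12 a visit always falls between relapse and omalizumab, so no event is lost and the change lies between −0.88 and 0. The f = 0 column depends somewhat on how the users without relapse are drawn; a variant gives −0.65 to −0.47. Over 72 combinations (60, 100 or 160 remitters; 4, 8, 12 or 16 users; L of 2, 4 or 8; 30% or 50%), the sign turns positive once 14% to 44% of users had an earlier UAS7 above 6.

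**6. An extreme case.** Suppose 5, 10 or 17 users among 60 to 140 remitters all have their first UAS7 above 6 inside the gap, and 20% or 40% of the other remitters relapse. The estimate then rises by about 3 to 25 points. This is larger than in step 5 because every user's event is lost by construction.

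**7. Other analyses.** In the weekly response rates, a deleted week with UAS7 above the threshold is non-response under either rule. Only gap weeks at or below the threshold change, from response to non-response under Section 4. Rates at scheduled visits agree unless omalizumab starts on a visit day. Mean weekly scores lose the gap weeks.

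**The case against.** The best defence is that the Section 4 bullet is leftover summary wording. Five statements in Section 2.6 use the omalizumab start, and a programmer working from the methods text would probably do the same. Section 4 also carries two treatment-emergent definitions side by side, one with the 16-week limit and one without, so it is not a tidy source. This is plausible, but no precedence is stated, and a section that records changes to the planned analyses is one a programmer would reasonably follow.

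No event is lost on two readings. First, Protocol 3.1 provides for an ad-hoc visit when UAS7 reaches 12. If that counts as the last visit and falls before the start day, the relapse is kept. But a score above 6 and below 12 need not trigger such a visit, and one on the omalizumab start day is not before it. Second, if scores exist only at visits, as the by-visit language in 2.6 and the seven days before a visit in 2.6.2 and 2.6.10 could suggest, nothing lies in the gap. That sits poorly with the weekly definitions in 2.1.3 and 2.6.10. The SAP settles neither reading.

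Table 1-4 also equates sustained remission with achieving UAS7 of 6 or less, and the response-rate version is not inflated because users count as non-responders up to Week 100. That is correct. The inflation concerns only the time-to-loss curves, but the response-rate tables are not visibly limited to Week 52 remitters.

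Three further points stand. Parts of the SAP are redacted, so the lack of a precedence rule refers to visible text. The efficacy analyses are descriptive. The primary safety analysis uses all data regardless of omalizumab.

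**Conclusion.** The concern holds. The SAP contains two incompatible cut-offs for the same scores in the same patients, with no visible rule to choose between them. Read with weekly scores and scheduled visits, Section 4 can turn a recorded relapse into a censored remission in the analysis serving the only secondary objective.

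The actual effect cannot be computed from the documents. Under the step 5 assumptions it runs from about −0.9 to +3.5 points at Week 100. Users with an earlier UAS7 above 6 in the gap push the estimate up; users without one are only censored sooner, which pushes it slightly down. A net upward shift is more likely because the protocol ties other therapy to relapse, but this is not established. The point should be fixed, but it does not touch the primary objective.

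**What to change.** In the Section 4 bullet, for HSS, ISS and UAS, replace the last visit before omalizumab with the omalizumab start date. The bullet then agrees with 2.6.1 to 2.6.3 and 2.6.10. It also fits the aim stated in 2.6.10, which is to remove bias from omalizumab use; scores recorded before omalizumab cannot carry that bias. Because 2.6.10 limits time-to-loss censoring to patients still maintaining response, a UAS7 above 6 or a loss of response before omalizumab then counts as an event.

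The cost is one phrase, with no new analysis and no edit to Section 2.6. The redacted variables in the same bullet cannot be judged and are outside this change. Section 2.6.10 also does not say whether the earlier or later of its two censoring dates applies; that is a separate point.
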